**Statistical Analysis:**

Descriptive analyses

The following tables will be presented:

- Baseline general population survey (GPS) process outcomes by city (refusal rate, sample size, % giving blood, urine, swabs)[[name] has done]

- Baseline STI rates (Ct, Gc, Syphilis, HIV, Trich, BV) in the GPS by city [[name] has done]
- 2006 GPS process outcomes by city (refusal rate, sample size, % giving blood, urine, swabs) [[name]]
- 2006 GPS demographics (age, gender, etc) by city [UW]
- 2006 GPS STI rates (Ct, Gc, Syphilis, HIV, Trich, BV) by city [UW]
- 2006 GPS rates of condom use among men with commercial sex partners in the last year, rates of condom use among men with male sex partners in the last year; rates of condom use among men and women with their last partner in the last 3 months; by gender [UW]
- Baseline female sex worker (FSW) survey process outcomes by city (refusal rate, sample size, % giving specimens) [[name] has done]
- Baseline STI rates (Ct, Gc, Syphilis, HIV, Trich, BV) in the FSW survey by city [[name] has done]
- 2006 FSW survey process outcomes by city (refusal rate, sample size, % giving specimens) [[name]]
- 2006 FSW demographics (age, workplace type, etc) by city [UW]
- 2006 FSW survey STI rates (Ct, Gc, Syphilis, HIV, Trich, BV) by city [UW]
- 2006 FSW rates of condom use at the last sexual encounter; by city; by intervention arm [UW]

The following graph will also be presented:

- FSW STI rates (Ct, Gc, Syphilis, HIV, Trich, BV) over time in the interventions cities, pooled [[name]]

### Inferential analyses

#### *Primary analysis*

The unit of analysis will be the city (i.e. STI prevalence at the city level). This approach is appropriate since the sample size is approximately the same from city to city. The primary analysis of intervention efficacy will be based on the model

$$d_i^O = b_0 + b_1 d_i^B + \epsilon_i \quad (M1)$$

where  $d_i^O$  is the difference in the primary STI endpoint (combined gonorrhea, chlamydia and syphilis prevalence) between the intervention and control communities (control – intervention) of the  $i$ th pair in the final (2006) outcome survey,  $d_i^B$  is the corresponding difference in the baseline survey and  $\epsilon_i$  is a random error. The hypothesis of interest is

$$\begin{aligned} \text{Ho: } b_0 &= 0 && \text{(no intervention effect)} \\ \text{Ha: } \beta_0 &\neq 0 && \text{(intervention effect)} \end{aligned} \quad (H1)$$

Note that if  $d_i^B$  was not included in the model, this analysis would be equivalent to a paired t-test. The  $d_i^B$  term is included in the model to control for differences in STI prevalence at baseline (which may occur in spite of the matching).

Least squares regression will be used for model fitting. The standardized test statistic  $\hat{b}_0 / se(\hat{b}_0)$  from this analysis has a t-distribution with 8 degrees of freedom. A p-value will be reported for the hypothesis (H1) and a type I error rate ( $\alpha$ ) of 0.05 (two-tailed) will be used to reject/fail to reject the null hypothesis (H1).

The endpoint in the primary analysis will be **ctgcsy** as measured in the GP.

#### Secondary analysis

The analysis outlined above will also be used for the following endpoints:

- **Ctgsy** in FSW
- **Ctresul, ggresul, newsyph, tvresul, HIVresul, BV** in GPS
- **Ctresul, ggresul, newsyph, tvresul, HIVresul, BV** in FSW
- **Nocondl** in GPS
- **Culinter** in FSW

To determine if the intervention is more effective in particular subsets of individuals (i.e. those who prefer to use pharmacies for treatment of STI-related symptoms) we will use an individual level analysis of the 2006 GPS data based on the following model

$$\text{logit}(p_{ij}) = b_0 + b_1T_i + b_2B_i + b_3X_{ij} + b_4T_iX_{ij} + a_i$$

where  $T_i$  is a 0/1 treatment indicator for city  $i$ ,  $B_i$  is the baseline disease prevalence for city  $i$ ,  $X_{ij}$  is a 0/1 covariate indicating whether subject  $j$  in city  $i$  belongs to the subset of interest (i.e. uses FSW) and  $a_i$  is a random city effect ( $a_i \sim N(0, \sigma^2)$ ). The outcome in this analysis will be **ctgcsy**. In the absence of the interaction term, the  $b_1$  coefficient from this model estimates the overall treatment effect (comparable to  $b_0$  in model H1). With the interaction term in the model, the hypothesis  $H_0: b_4 = 0$  will be used to test if the intervention effect on **ctgcsy** differs across levels of  $X$  (e.g. we might expect  $b_4$  to be positive – intervention more effective – in individuals who prefer to use pharmacies for treatment of STI-related symptoms). A two-sided 0.05 level test will be used.

- To determine if the effectiveness of the intervention differs in individuals who prefer to use pharmacies for STI-related symptoms,  $X_{ij} = \text{hlthseek}$ .
- To determine if the effectiveness of the intervention differs in men who use FSW,  $X_{ij} = \text{sexfsw}$  and the analysis is restricted to men

Formatted: Bullets and Numbering

**Dummy Tables:**

**General Population Survey (GPS) Process Outcomes**

[figure not shown]
City	Invited to participate	Refusal rate	Provided questionnaire data, n(%)	Provided blood, n(%)	Provided Genital Samples		
					Males	Females	
					Urine, n(%)	Urine, n(%)	Vaginal swabs, n(%)
Ayacucho							
Barranca							
Cajamarca							
Chimbote							
Chincha							
Cusco							
Huancayo							
Huanuco							
Huaraz							
Ica							
Ilo							
Iquitos							
Juliaca							
Pasco							
Piura							
Pucallpa							
Tacna							
Talara							
Tarapoto							
Tumbes							
Intervention cities							
Control cities							
Total							

## GPS Demographic Data

City	Age mean (range)	% male	<3 years in this city	Can read/ write?	Ever had sex?	Ever married/ cohab?	Living w/ sex partner
Ayacucho							
Barranca							
Cajamarca							
Cerro de Pasco							
Chimbote							
Chincha							
Cusco							
Huancayo							
Huanuco							
Huaraz							
Ica							
Ilo							
Iquitos							
Juliaca							
Piura							
Pucallpa							
Tacna							
Talara							
Tarapoto							
Tumbes							
Intervention cities							
Control cities							
Overall							

**Selected GPS Behavioral data - 2006**

Gender	Ever had sex	Would use pharmacy for abnormal secretion	Condom use with last ptr	Sex with FSW	Condom with FSW	Sex with male	Condom with male
Male							
Female							
Overall							

### FSW Survey Demographic Data

City	Age mean (range)	Can read or write (%)	Ever married or cohabitant (%)	Living w/ sex partner (%)	Have dependen ts (%)	Charged to last client mean (range)
Ayacucho						
Barranca						
Cajamarca						
Cerro de Pasco						
Chimbote						
Chincha						
Cusco						
Huancayo						
Huanuco						
Huaraz						
Ica						
Ilo						
Iquitos						
Juliaca						
Piura						
Pucallpa						
Tacna						
Talara						
Tarapoto						
Tumbes						
Intervention cities						
Control cities						
Overall						

**STI Rates (one table for GPS, one for FSW)**

Arm	City 	N 	Ct 	Gc 	Syph 	HIV 	N(female) 	Trich 	BV 
C	Ayacucho								
I	Cajamarca								
C	Talara								
I	Chincha								
C	Huancayo								
I	Cusco								
C	Tarapoto								
I	Huanuco								
C	Tacna								
I	Ica								
C	Barranca								
I	Pasco								
C	Huaraz								
I	Pasco								
C	Chimbote								
I	Piura								
C	Iquitos								
I	Pucallpa								
C	Ilo								
I	Tumbes								
C	Control								
I	Intervention								
	Total								

Notes:

N is approximate for any given outcome since there may have been a few insufficient, lost or damaged specimens.

Chlamydia by PCR (Aptima)

Gonorrhea by PCR (Aptima)

Syphilis by RPR (> 1:8)

HIV by Elisa x 2 with WB confirmation

Trichomonas by culture (In-Pouch)

BV by ?

Cities are arranged in pairs

## PREVEN Trial Data Analysis Plan

**Title:** PREVEN Community Randomized Trial – A hybrid HIV/STD intervention on a high-risk group of female sex workers (FSW) and on the lower-risk young adult general population.

### **Background and Overview:**

The primary aim of this trial is to evaluate the impact of a hybrid STD/HIV prevention intervention on the prevalence of sexually transmitted infections (STIs) (including gonorrhea, chlamydia, trichomonas, syphilis and HIV) in female sex workers (FSW) and the young adult general population (GP). The study is designed as a prospective community randomized trial of 20 medium sized cities in Peru. The intervention was begun in 2003 and the primary outcome (STI prevalence) will be measured in two cross sectional surveys (one in a population of FSW and the other in the general population of young adults) in 2006 in each of the 20 Peruvian cities. The surveys will also provide us with estimates of the fraction of HIV cases that are diagnosed and treated in existing programs (Ministry of Health, Army, Navy, Police health services, Social Security system and other programs in Peru), the prevalence of HIV viremia, the prevalence of bacterial vaginosis (BV) and risk behaviors. In secondary analyses we will use this information to identify characteristics of bridging populations and determining the structure of sexual networks. This information will be directly useful for planning nationwide programs that integrate prevention and treatment.

**Broad objective:** To evaluate the impact of a hybrid STD/HIV preventive intervention CRT on the prevalence of sexually transmitted infections (STIs), gonorrhea, chlamydia, trichomonas, and syphilis, in a high-risk group of female sex workers (FSW) and in the lower risk young adult general population.

### **Specific aims:**

#### Primary

- To evaluate the impact of a hybrid STD/HIV preventive intervention on the combined prevalence of gonorrhea and/or chlamydia and/or syphilis ( $RPR \geq 1:8$ ) and/or trichomonas (in women) in the general population of young adults.

#### Secondary

- To evaluate the impact of a hybrid STD/HIV preventive intervention on the combined prevalence of gonorrhea and/or chlamydia and/or syphilis ( $RPR \geq 1:8$ , TP•PA confirmed) and/or trichomonas in female sex workers.
- To evaluate the impact of a hybrid STD/HIV preventive intervention on the prevalences of bacterial vaginosis and HIV in the general population of young adults.
- To evaluate the impact of a hybrid STD/HIV preventive intervention on the prevalences of bacterial vaginosis and HIV on female sex workers.
- To evaluate the impact of a hybrid STD/HIV prevention intervention on condom use in the GP and FSW
- To determine if the effectiveness of the intervention differs in GP individuals who prefer to use pharmacies for treatment of STI-related symptoms
- To determine if the effectiveness of the intervention differs in GP men who use FSW

### **Study Design:**

**Overview:** The study is a community randomized trial of 20 medium sized cities in Peru. The cities were initially paired based on STI prevalence measured in a baseline (pre-intervention) survey. One member of each pair was then randomized to receive the intervention, which consists of two primary components: i) pharmacist education to strengthen syndromic management of STI, and ii) outreach to female sex workers (FSW) using a mobile team. The primary outcome (STI prevalence) will be measured in two cross

sectional surveys - one among FSW and the other in the general population of young adults - in each of the 20 Peruvian cities after the intervention has been in place for approximately 2 years.

**Baseline Surveys:** Baseline surveys of STI prevalence in the general population (18-29 year old men and women), FSW and their clients were conducted in 24 midsize (> 50,000) cities in Peru in 2002 and 2003. These surveys collected both behavioral information and biologic samples.

The general population survey (GPS) used year 2000 census data to randomly select households by cluster sampling (each cluster was an average of 40 households). A random sample of clusters was selected for each city. Then a census was conducted for each household in the selected clusters and a random sample of households with eligible members was selected. Within each selected household, one eligible individual (male or female, aged 18 - 29, living in the city for at least 6 months) was randomly selected.

The FSW/client surveys used time-venue sampling. In each city the study team mapped known locations of FSW. Each day of the week was then divided into x parts and a random sample of time/venues was selected. All (?) sex workers present at the chosen venue at the chosen time were invited to participate in the survey.

**Randomization:** From the 24 cities that took part in the 2002 general population and 2003 FSW and client surveys, twenty were selected to participate in the CRT. Matching was employed to reduce imbalances in the randomization. Matching was based primarily on total STI prevalence (chlamydia, trichomoniasis, syphilis, gonorrhea, HIV) in the baseline general population survey. Population size and location (coastal, highland, jungle) were used as secondary matching criteria. Ten cities (one member of each matched pair) were then randomized to receive the intervention. Table 2 shows the matched pairs.

[figure not shown]
**Table 2. Matched city pairs for the PREVEN project**

Matched pairs		
1	Chimbote	Piura
2	Ilo	Tumbes
3	Ayacucho	Cajamarca
4	Tacna	Ica
5	Huaraz	Cerro de Pasco
6	Huancayo	Cuzco
7	Talara	Chincha
8	Tarapoto	Huanuco
9	Iquitos	Pucallpa
10	Barranca	Juliaca

**Intervention:** The intervention consists of two key components: 1) training and support of pharmacy workers and referral networks of STD clinicians for improved STI recognition and management and for STD/HIV prevention counseling (RED PREVEN component); and 2) outreach to FSW via mobile teams (consisting of a health worker and a peer FSW educator) to increase STI screening and treatment, and condom use (FSW component). The intervention began in July 2003 and will continue through (at least) the final outcome surveys (December 2006). To supplement both intervention components, the study also included a one-year (October 2003 – October 2004) social marketing campaign of condoms with the provision of STD treatment packets and promotion of condoms' double protection against STDs/HIV and unwanted pregnancy.

Outcome Surveys: Interim surveys of the GP and FSW were conducted in 2005 and final outcome surveys will be conducted in 2006. The format and content of the surveys will be similar to the baseline surveys described above although the questionnaire data will be collected using a handheld (Palm) computer.

The figure below shows the timeline of the various components of the study.

**Testable hypotheses:** The testable hypotheses for this study will have the form

$$H_0: p_{\text{control}} = p_{\text{intervention}}$$

$$H_a: p_{\text{control}} \neq p_{\text{intervention}}$$

where  $p_i$  is the prevalence of the outcome (combined or individual STIs) in the  $i$ 'th group. The section on inferential analysis below contains details on how this hypothesis will be tested.

**Variables:**

The following table lists variables that will be used in the statistical analyses.

Variable	Definition	How collected	Units	Use in analysis
pcrcturine	CT in urine by PCR	GPS	0 = negative; 1 = positive; 2 = indeterminate	Outcome component
pcrctswab	CT in vaginal swab by PCR	GPS	0 / 1 / 2	Outcome component
Ctresul	Prevalence of Chlamydia infection by PCR	Urine samples tested by Cobas (baseline) or Aptima (2006); result of each test is positive or negative and individual results are aggregated to the city level*  FSW: variable arrived as 0/1/5 (5= indeterminate) in 2006, with description: “chlamydia trachomatis cobas result”. Indeterminates treated as missing.  GPS: Created variable for 2006 such that: vaginal swab results used where swab provided; otherwise urine result used. For men all samples were urine. Indeterminate results treated as missing.	0 - 1	Outcome
Pcrgcurine	GC in urine by PCR	GPS	0 / 1 / 2 (2= indeterminate)	Outcome component
Pcrgcswab	GC in vag. swab by PCR	GPS	0 / 1 / 2	Outcome component
Genprgcuri	GC in urine by PCR (Genprobe)	GPS	0 / 1 / 2	Outcome component
Genprgcswa	GC in swab by PCR (Genprobe)	GPS	0 / 1 / 2	Outcome component
taqmangcur	Taqman GC in urine	GPS - received variable in 2006 but contained no data – will we use this?	?	Didn't use
taqmangcsw	Taqman GC in swab	”	?	Didn't use
Ngresul	Prevalence of gonorrhea infection by PCR	Urine samples tested by Cobas (baseline) or Aptima (2006); result of each test is positive or negative and individual results are aggregated to the city level*  FSW: variable arrived as 0/1/5 (5=	0 - 1	Outcome

		
indeterminate) in 2006 with description: “neisseria gonorrhoea cobas result confirmed by aptima”. Indeterminates treated as missing.
 
GPS: Created variable from other variables received in 2006 so that: Vaginal swab results used where women provided swab; otherwise result from urine sample used. For men urines used. We required positives to be confirmed by Genprobe. Indeterminates and positives without available confirmation results were treated as missing.
		
NewSyph	Prevalence of elevated serum titer indicating recent syphilis infection	
Blood samples tested by RPR and confirmed by TPPA; result of each test is positive (titer <math>\geq</math> 1:8) or negative (titer < 1:8) and individual results are aggregated to the city level*.
 
GPS and FSW: Created variable in 2006 to accomplish this, using rpr, rpr dilution and tppa results.
	0 - 1	Outcome
HIVresul	Prevalence of HIV infection	
Blood sample tested by dual ELISA and confirmed by WB; result of each test is positive or negative and individual results are aggregated to the city level*
 
FSW: variable arrived as 0/1/5 (5= indeterminate) in 2006 with description: “hiv result”. Indeterminates treated as missing.
 
GPS: created variable to match above description, from separate wb and elisa results.
	0 - 1	Outcome
Tvresul	Prevalence of trichomonas infection	Urine samples tested by InPouch culture (baseline) or Aptima (2006); result of each test is positive or negative and individual results are aggregated to the city level* (female only)	0 - 1	Outcome
BV	Prevalence of bacterial vaginosis	??; result of each test is positive or negative and individual results are aggregated to the city level* (female only)	0 - 1	Outcome
CtGcSy	Prevalence of	GPS and FSW: Created from	0 - 1	Primary

	Chlamydia and/or gonorrhea and/or syphilis infection	ctresult, gresult, newsyph and aggregated to city level* If any of the 3 test results was missing, combined outcome treated as missing.		outcome
City	City code	assigned	1 - 20	
Arm	Randomization arm	assigned	0 = control 1 = intervention	Primary predictor
Pair	Randomization pair	assigned	1 - 10	Stratification variable
Age	Age (yrs)	GPS FF Q1.2		Covariate
Gender	Gender	GPS FF Q1.1	1=male 2=female	Covariate
Read	Can you read?	GPS FF Q1.4	1=yes 2=no 9=no response	
Married/Cohab	Marital status	GPS FF Q7.1	1=Single 2=Married 3=Cohabiting 4=Separated 5=Divorced 6=Widow/er 9=No response	
Eversex	Ever had sex:	GPS SA Q1.11 (female) Q1.12 (male)	0=no/1=yes	
Sexfsw	Sex w/prostitute:	GPS SA Q2.6 (males only, who replied 'yes' to 'eversex'),	0=no/1=yes	
Sexfswnum	How many times sex w/prostitute in last 12 months:	GPS SA Q2.9 (males only, who replied 'yes' to 'sexfsw')	0=None; 1-10=actual #; 11=more than 10; 66=doesn't remember	
Sexfswnocondom	How many times sex w/ prostitute w/o condom in last 12 months	GPS SA Q2.10 (males who gave response of 1 or more to 'sexfswnocondom');	1-4=actual #; 5=more than 4; 6=Always uses condom; 66=Doesn't remember	
Nocondc	Noncondom use w/ prostitute in last 12 months (men only):	Created variable Omission in code creating variable for interim analysis caused rates to be dramatically overestimated; See note.	1=yes (had sex with prostitute without condom in last year); 0=no (always used condom or no sex with prostitute)	Outcome

Sexmsm	Sex with male	GPS SA Q2.11 (males only)		
Msmnum	How many times sex w/male	GPS SA Q2.14 (males only, but variable "msmnum" received at interim analysis shows everyone responding to this including women and men who did not acknowledge MSM. Looks like not correct data for this question.)	0=None 1-4=? 66=Doesn't remember	
Msmnocond	How many times sex w/male w/o condom	GPS SA Q2.15 (males only, and those who acknowledge MSM.)	1-4=actual #; 5= more than 4; 6=Always uses condom; 66=Doesn't remember	
Nocondm	Noncondom use with male in last 12 months (men only)	Created variable Omission in code creating variable for interim analysis was an oversight and led to overstating rates; see note.	1=yes (had sex with male without condom in last year); 0=no (always used condom or no sex with male)	Outcome
Sexlastpartnum	Number of times sex with last partner in last 3 months	GPS SA Q3.11	1-20=actual # 21=more than 20; 66=doesn't remember	
Sexlastpartnocondom	Number of times sex with last partner in last 3 months without condom	GPS SA Q3.12	1-20=actual # 21=more than 20; 22=always uses condom; 66=doesn't remember	
Nocondl	Noncondom use w/last partner (GPS)	Created variable	1=yes (had sex with last sex partner without condom in last year); 0=no (always used condom or no sex in last 3 months)	Outcome
hlthseek	Health seeking behavior – "If you had abnormal secretion ... what would you do first?"	GPS SA Q2.1	=Nothing =Consult friend =Pharmacy =Doc/Clinic =Hospital =Meds @ home =Other	
Workplace	Workplace type for	FSW questionnaire Q503 (last 7 days)	1=Brothel;	covariate

	FSW	or Q504 (last month)	2=Nightclub; 3=Bar; 4=Street; Other 99=no response	
Culinter	Condom use w/ last intercourse (FSW)	FSW questionnaire Q618 (is this only among women whose last sex was vaginal intercourse? – Q617?)	1=Yes 2=No (I created 'cl', same variable but 0=no/1=yes)	Outcome
	Can read/write?	FSW questionnaire – Q204	1=yes to both 2=can read 3=can write 4=neither	covariate
	Ever married or cohabitant?	FSW questionnaire – Q304	1=yes, 2=no, 99=no response	covariate
	Living with sex partner?	FSW questionnaire – Q309.  For FSW, Will make 0/1 variable (1,2,4=yes, 3 or 5=no)	1=married live w/spouse; 2=married live with other sex ptr 3=married not living with sex ptr 4=not married, cohab; 5 = not married not cohab 99=no response	covariate
	Have dependents?	FSW questionnaire – Q310	1=yes, 2=no, 99=no response	Covariate
	Charged last client	FSW questionnaire – Q616 if last sex partner was client. If second to last sex partner was last client, then Q629. If sex partner before that, then Q643		

\* To aggregate results to the city level the number of positive results in a given city/survey are divided by the number of nonmissing results from that city/survey.

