## **Gonococcal Infection**

REVISIONX: Specimens from 2002-2003 and 2005 surveys reported as gonorrhea positive in the AMPLICOR assay, according to manufacturer's instructions, were further tested by the Gen-Probe APTIMA assay, utilizing specimens suspended in 2SP, allowing final classification as positive or negative based upon the APTIMA assay. Specimens from the 2006 survey were tested first by the APTIMA assay and then all positive specimens were tested by the AMPLICOR assay. Positive results are confirmed by APTIMA testing of specimens suspended in 2SP. Gonococcal infection is defined by positive AMPLICOR plus positive APTIMA assays.

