## **Chlamydial Infection**

REVISIONY: Specimens from the 2002-2003 and 2005 surveys reported as indeterminate by Roche AMPLICOR were tested by the Gen-Probe APTIMA Combo 2 Assay (Gen-Probe, San Diego, CA). The 2006 survey employed initial testing by the Gen-Probe Aptima assay utilizing the specimen collected in APTIMA transport medium; all positive specimens then were tested by the AMPLICOR assay performed on the specimen eluted in 2SP.

Results from the 2002-03 and 2005 surveys are considered positive if initially AMPLICOR positive; or if initially indeterminate and subsequently positive in the APTIMA assay. Specimens from the 2006 survey positive by both assays are considered positive. Those specimens yielding discordant results undergo APTIMA re-testing of specimens suspended in 2SP, for final classification as positive or negative. For these specimens, chlamydial infection is

---

X Rationale for revision: Target sequences in the methyltransferase gene of *N. gonorrhoeae* used in the AMPLICOR assay have been shown to be present in other *Neisseria* species and "false-priming" has been suggested with lactobacilli in this assay. In interim analysis, prior to unblinding of the data, we found that while 70% and 48% of urine and clinician-collected samples were APTIMA positive, respectively, only 12% of self-collected vaginal swab AMPLICOR positive specimens were positive for gonorrhea in the APTIMA assay. Those specimens AMPLICOR positive and APTIMA negative were much more likely to have had lower AMPLICOR optical density readings than were specimens positive in both tests (data not shown). This finding is consistent with previous reports associating apparent false-positive AMPLICOR results with lower test signal strengths.

Y Although studies have shown quite similar sensitivity and specificity of the Roche AMPLICOR and Gen-Probe APTIMA assays for chlamydial infection, the AMPLICOR assay yields an important proportion of specimens

defined by positive results in the APTIMA assay performed on the 2SP-suspended specimen. (See Appendix A: Laboratory Flow Charts).

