**Definitions**

**Positive** – Initially positive in both the Aptima and Roche assays or positive in the Aptima assay performed on the 2SP-suspended specimen from individuals positive or equivocal in the Aptima assay and negative or indeterminate in the Roche assay.

**Negative** – Initially negative in the Aptima assay or negative in the Aptima assay subsequently performed on the 2SP-suspended specimen.

Trichomoniasis

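### The SAP's 2006 general-population chlamydia and gonorrhoea derivations do not implement the protocol's 2006 APTIMA-first algorithm with 2SP retest

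*Supplement*

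**What the plan says.** **Protocol, 2006 test order.** Under Laboratory Methods, Gonococcal Infection: "Specimens from the 2006 survey were tested first by the APTIMA assay and then all positive specimens were tested by the AMPLICOR assay". Under Chlamydial Infection, after an initial APTIMA test: "all positive specimens then were tested by the AMPLICOR assay performed on the specimen eluted in 2SP". Discordant chlamydia specimens are then retested by APTIMA on the 2SP-suspended specimen, and that retest decides.

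**Protocol, Appendix A, 2006 definitions for both organisms.** A specimen is negative if "Initially negative in the Aptima assay or negative in the Aptima assay subsequently performed on the 2SP-suspended specimen". It is positive if both assays are positive. It is also positive if APTIMA was positive or equivocal, AMPLICOR was negative or indeterminate, and the APTIMA retest on 2SP is positive.

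**Latest Data Analysis Plan, Variables table, GPS.**
- *Ctresul*: "vaginal swab results used where swab provided; otherwise urine result used", with indeterminate results set to missing. The only chlamydia components listed are `pcrcturine` ("CT in urine by PCR") and `pcrctswab`. No Gen-Probe chlamydia variable is listed.
- *Ngresul*: built from other variables, swab before urine in women; "We required positives to be confirmed by Genprobe". Then: "Indeterminates and positives without available confirmation results were treated as missing".
- Both rows open with "Urine samples tested by Cobas (baseline) or Aptima (2006".
- City prevalence is positives divided by nonmissing results. The table's only composite row is set to missing if any component is missing.

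**The concern.** The gonorrhoea rule is written in the order of the 2002–03 and 2005 surveys, when AMPLICOR screened and APTIMA confirmed. In 2006 that order was reversed. The chlamydia rule has no second assay and no retest, although the protocol's 2006 case definition needs both. An analyst working from the SAP therefore cannot reproduce that definition, and has to decide at the coding stage how discordant, equivocal and indeterminate specimens are scored.

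Chlamydia is a main component of the primary composite. Baseline prevalence was 4.0% in men and 6.8% in women, against 5.2% for trichomonas, which was measured in women only. The primary model M1 rests on ten pair differences with 8 degrees of freedom, so reclassifying a few people per city enters the test directly.

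**Working it through.** **1. Classification of 2006 chlamydia specimens.** The SAP does not say which assay fills `pcrct*`, so two single-assay readings are set beside Appendix A. Equivocal is taken to be coded as indeterminate.

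| Result pattern | Appendix A | SAP, field = AMPLICOR, APTIMA negatives set to 0 | SAP, field = initial APTIMA |
|---|---|---|---|
| APTIMA negative | 0 | 0 | 0 |
| APTIMA positive, AMPLICOR positive | 1 | 1 | 1 |
| APTIMA positive, AMPLICOR negative, 2SP positive | 1 | **0** | 1 |
| APTIMA positive, AMPLICOR negative, 2SP negative | 0 | 0 | **1** |
| APTIMA positive, AMPLICOR indeterminate | retest result | **missing** | 1, **wrong if retest negative** |
| APTIMA equivocal, AMPLICOR negative | retest result | 0, **wrong if retest positive** | **missing** |

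Each reading departs from the protocol, in different cells.

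**2. Gonorrhoea.** The latest SAP prints no code. A Stata comment beside the same rule in an earlier copy sets the result to 0 whenever Gen-Probe is 0, and to missing when PCR is 1 with no Gen-Probe result. Running that logic over the combinations gives:
- PCR missing, Gen-Probe 0: scored 0, so APTIMA negatives are kept.
- PCR 1, Gen-Probe 1: scored 1.
- PCR 0, Gen-Probe 1: scored 0, without use of the 2SP retest.
- PCR indeterminate, Gen-Probe 1: stays indeterminate, hence missing, where Appendix A uses the retest.

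**3. Share with no AMPLICOR result.** The documents state no figure to reproduce. Assumption: 2006 APTIMA positivity equals baseline prevalence. The female share of the baseline survey was 50.3%.
- Chlamydia positive: 0.497 × 0.040 + 0.503 × 0.068 = 0.0541. No AMPLICOR value: 1 − 0.0541 = 94.6%.
- At half baseline positivity: 97.3%. At twice: 89.2%.
- Gonorrhoea positive: 0.497 × 0.003 + 0.503 × 0.008 = 0.0055. No AMPLICOR value: 99.4%.

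These are shares without an AMPLICOR result. They are shares that cannot be scored only if the field holds AMPLICOR alone.

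**4. Size of the discordance effect.** With 86% of 600 giving specimens there are 516 per city, and 516 × 0.0541 ≈ 28 chlamydia positives. The documents give no rate of AMPLICOR disagreement. Assume 5–20%, with every such specimen positive on retest. Then 28 × 0.05 = 1.4 to 28 × 0.20 = 5.6 cases per city are lost under the AMPLICOR reading.

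M1 was simulated for chlamydia alone: 10 pairs, 500 per city, coefficient of variation .10, 30% reduction, two-sided t on 8 df.

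| Rule | Mean difference (control − intervention) | Power |
|---|---|---|
| Protocol definition | .0162 | .81–.82 |
| 5% of positives lost | .0155 | .81 |
| 10% lost | .0146 | .78 |
| 20% lost | .0129 | .74 |

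If the loss is equal in both arms, the relative reduction stays at 30%; the absolute difference that M1 tests shrinks.

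**The case against.** *The SAP may not mean AMPLICOR by PCR.* This stands in part. The Ctresul and Ngresul cells name Aptima for 2006, and the table labels Gen-Probe gonorrhoea results as PCR too. If `pcrct*` holds the APTIMA screening result, everyone has a value. The mismatch then moves to the last column of the first table: people negative on the 2SP retest are counted as infected. Only a field delivered already resolved by the full algorithm would agree with Appendix A, and no text says that it was.

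*The gonorrhoea rule largely agrees with the protocol.* This stands in part. The Gonococcal Infection section defines infection as positive on both assays, which does not depend on test order. But Appendix A also counts specimens that were AMPLICOR-negative and positive on the 2SP retest. The two protocol statements therefore differ, and the SAP follows neither explicitly for discordant specimens.

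*The notes may describe 2005 data received in 2006.* Possible, since nearby rows mention the interim analysis. In that case the SAP would contain no GPS derivation for the survey that carries the primary endpoint.

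*The algorithm is already in the protocol.* True, but the SAP states a different rule, and where specimens are discordant both cannot be followed.

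A reader might go further and infer that about 95% of participants have no value to score, that power falls to the type I error rate, or that Gen-Probe confirmation is applied to chlamydia. The documents do not support these. The first two require an AMPLICOR-only field, which no text states. For gonorrhoea, the printed code scores Gen-Probe negatives as 0, so mass missingness does not arise. The confirmation sentence belongs to the gonorrhoea row only.

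**Conclusion.** The SAP's 2006 GPS rules for Ctresul and Ngresul do not implement the protocol's 2006 case definition. For chlamydia the disagreement concerns specimens that are APTIMA-positive or equivocal without a matching AMPLICOR positive. True positives are lost if the field is AMPLICOR with APTIMA negatives set to 0; retest negatives are counted as cases if it is the initial APTIMA result. For gonorrhoea the gap is the missing 2SP retest and a test order carried over from the earlier surveys; at 0.3% in men and 0.8% in women at baseline, it weighs less.

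The size is uncertain because the documents give no discordance rate. Under the assumed 5–20%, chlamydia-only power is .81 to .74, a modest loss. None is shown for the composite, whose tabulated power is .99 at a 30% reduction (one-tailed). The figure of about 95% without a chlamydia value (89–97% at 2 to 0.5 times baseline positivity) is conditional on an AMPLICOR-only field. The case for acting is that two stated outcome rules conflict in a main component of the primary endpoint.

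**What to change.** In the SAP's Variables table:

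1. State which assay fills `pcrct*` and `pcrgc*` in the 2006 survey.
2. Derive 2006 Ctresul and Ngresul by the Appendix A rule: initial APTIMA negative = 0; APTIMA and AMPLICOR both positive = 1; APTIMA positive or equivocal with AMPLICOR negative or indeterminate = result of the APTIMA retest on 2SP.
3. Add the APTIMA chlamydia variables (swab and urine) and the 2SP-retest variables for both organisms.
4. Limit the rule of a PCR positive confirmed by Gen-Probe to the 2002–03 and 2005 gonorrhoea results.
5. Reconcile the both-positive definition under Gonococcal Infection with the 2006 definitions in Appendix A.

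The cost is SAP wording and a few lines of derivation code. No new laboratory work is needed if the 2006 testing was carried out as the protocol describes.
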